##### One month post-vaccination (D30) in all participants:

- Anti-PRP Ab concentrations
- Anti-PRP Ab concentrations  $\geq$  0.15  $\mu$ g/mL and  $\geq$  1.0  $\mu$ g/mL
- Anti-poliovirus (types 1, 2, and 3) Ab titers

- Anti-poliovirus (types 1, 2, and 3) Ab titers  $\geq 1:8$
- Anti-pertussis (PT, FHA, PRN, and FIM) Ab concentrations
- Anti-pertussis (PT, FHA, PRN, and FIM) vaccine response\*
  - \* Pertussis vaccine response definition:
    - Pre-vaccination  $<$  LLOQ, then post-vaccination should be  $\geq 4$ x the LLOQ
    - Pre-vaccination  $\geq$  LLOQ but  $<$  4x the LLOQ, then post-vaccination should achieve a 4-fold rise (post-vaccination/pre-vaccination  $\geq 4$ )
    - Pre-vaccination  $\geq$  4x the LLOQ, then post-vaccination should achieve a 2-fold response (post-vaccination/pre-vaccination  $\geq 2$ )
- Anti-diphtheria toxoid Ab concentrations
- Anti-diphtheria toxoid Ab concentrations  $\geq 0.1$  IU/mL and  $\geq 1.0$  IU/mL
- Anti-tetanus toxoid Ab concentrations
- Anti-tetanus toxoid Ab concentrations  $\geq 0.1$  IU/mL and  $\geq 1.0$  IU/mL

### ***Infants***

#### Before first vaccination in all participants (D0)\*:

- Anti-rotavirus serum immunoglobulin (Ig) Ab concentrations
- Anti-pertussis (PT, FHA, PRN, and FIM) Ab concentrations
- Anti-diphtheria toxoid Ab concentrations
- Anti-tetanus toxoid Ab concentrations

#### One month after 6 MoA vaccination (D150) in all participants:

- IgG Abs against hepatitis B surface antigen concentration  $\geq 10$  mIU/mL and  $\geq 100$  mIU/mL
- Anti-PRP Ab concentrations
- Anti-PRP Ab concentrations  $\geq 0.15$   $\mu$ g/mL and  $\geq 1.0$   $\mu$ g/mL
- Anti-poliovirus (types 1, 2, and 3) Ab titers
- Anti-rotavirus serum IgA Ab concentrations
- Anti-rotavirus serum IgA Ab concentrations with  $\geq 3$ -fold rise over baseline\*
- Anti-pertussis (PT, FHA, PRN, and FIM) Ab concentrations
- Anti-diphtheria toxoid Ab concentrations
- Anti-diphtheria toxoid Ab concentrations  $\geq 0.01$  IU/mL and  $\geq 0.1$  IU/mL
- Anti-tetanus toxoid Ab concentrations
- Anti-tetanus toxoid Ab concentrations  $\geq 0.01$  IU/mL and  $\geq 0.1$  IU/mL

#### One month after 12-15 MoA vaccination (D330-D420) in all participants:

- Anti-measles Ab concentrations

[figure not shown]
---

\*Not applicable from protocol amendment V5.0

- Anti-measles Ab concentrations  $\geq$  255 mIU/mL
- Anti-mumps Ab concentrations
- Anti-mumps Ab concentrations  $\geq$  10 mumps Ab U/mL
- Anti-rubella Ab concentrations
- Anti-rubella Ab concentrations  $\geq$  10 IU/mL
- Anti-varicella Ab concentrations
- Anti-varicella Ab concentrations  $\geq$  5 glycoprotein enzyme-linked immunosorbent assay (gpELISA) units/mL

[figure not shown]
#### 4.2.2.3 Immunogenicity Assessment Methods

##### *Pneumococcal capsular polysaccharide - electro-chemiluminescent assay (PnPS-ECL)*

[figure not shown]

This method will be performed on BL0001 and BL0002 collected from toddlers, and on BL0001\*, BL0002, BL0003, and BL0004 collected from infants.

##### *Multiplexed opsonophagocytic killing assay (MOPA)*

[figure not shown]

\* Not applicable from protocol Version 5.0

[figure not shown]
This method will be performed on BL0001 and BL0002 collected from toddlers, and on BL0002, BL0003 and BL0004 collected from a subset of infants.

***Anti-Diphtheria, Tetanus, and Pertussis Antibodies***

This method will be performed on BL0001\* and BL0002 collected from both toddlers and infants.

***Anti-Haemophilus influenza type b (Anti-PRP) Antibodies***

[figure not shown]

This method will be performed on BL0001 and BL0002 collected from toddlers and on BL0002 from infants.

---

[figure not shown]
\* Not applicable from protocol Version 5.0 for infants

*Anti-Polio (types 1, 2, and 3) Antibodies*

[figure not shown]
This method will be performed on BL0001 and BL0002 collected from toddlers and on BL0002 from infants.

*Anti-Rotavirus IgA Antibodies*

[figure not shown]
This method will be performed on BL0001\* and BL0002 collected from infants.

*Anti-Hepatitis B Antibodies*

[figure not shown]
---

\* Not applicable from protocol Version 5.0

[figure not shown]
This method will be performed on BL0002 collected from infants.

*Anti-Measles Antibodies*

[figure not shown]
This method will be performed on BL0004 collected from infants.

*Anti-Mumps Antibodies*

This method will be performed on BL0004 collected from infants.

*Anti-Rubella Antibodies*

This method will be performed on BL0004 collected from infants.

*Anti-Varicella Antibodies*

This method will be performed on BL0004 collected from infants.

## 4.3 Derived Endpoints: Calculation Methods

### 4.3.1 Safety

#### 4.3.1.1 Solicited Reactions

##### 4.3.1.1.1 Daily Intensity

All daily records for solicited reactions will be derived into daily intensity according to the following classification: None, Grade 1, Grade 2, Grade 3, or Missing (Unknown).

For the derivation of daily intensities, the following sequential steps will be applied:

- 1) Solicited reactions (except Fever/Pyrexia) with an investigator presence recorded as “No” and with all daily records missing (Unknown) then all daily intensities will be derived as None (applicable only for Stage II using DC).
- 2) For non-measurable solicited reactions, daily intensities will correspond to daily records reported in the clinical database. For measurable solicited reactions the daily measurements reported in the clinical database will be converted based upon the intensity scales defined in the protocol; this assumes a reaction that is too large to measure (non-measurable, “NM”) is Grade 3.

Note: The maximum intensity on the ongoing period is derived from the record of the maximum intensity/measurement after the end of the solicited period following the rule described above.

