12.3 Handling of Missing Data and Outliers

12.3.1 Safety

No replacement will be done. Nevertheless, missing relationship will be considered as related at the time of stat analysis. Details will be described in the SAP.

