##### 4.3.1.1.2 Maximum Overall Intensity

Maximum overall intensity is derived from the daily intensities computed as described in Section 4.3.1.1.1 and is calculated as the maximum of the daily intensities over the period considered.

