##### 4.3.1.1.3 Presence (Occurrence)

Presence is derived from the maximum overall intensity over the time period considered:

- None: No presence
- Grade 1, Grade 2, or Grade 3: Presence
- Missing or Unknown: Missing presence

Participants with at least one non-missing presence for a specific endpoint will be included in the analysis. Conversely, those without a non-missing presence will not be included in the analysis of the endpoint.

The time period is displayed as D0-D3, D4-D7, D8 and later.

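### For Stage II solicited reactions other than fever, an investigator 'Yes' with no daily records drops out of the analysis while the matching 'No' counts as no reaction

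*SAP*

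**What the plan says.** SAP 4.3.1.1.1 derives daily intensities in sequential steps. Step 1 takes any solicited reaction apart from fever for which the investigator answered 'No' on presence and the diary holds no value for any day: "then all daily intensities will be derived as None (applicable only for Stage II using DC". It therefore has two limits: it applies to Stage II only, and it leaves fever out.

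Step 2 covers everything else. "For non-measurable solicited reactions, daily intensities will correspond to daily records reported in the clinical database", and measurable reactions are graded from the recorded measurements. The investigator's presence field plays no part in this step.

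The remaining rules follow from the daily intensities:

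- Maximum overall intensity (SAP 4.3.1.1.2) "is calculated as the maximum of the daily intensities over the period considered".
- Presence (SAP 4.3.1.1.3) is read from that maximum. The entry "None: No presence" keeps the participant as a non-event, and a missing maximum gives missing presence.
- For the denominator, "those without a non-missing presence will not be included in the analysis of the endpoint" (SAP 4.3.1.1.3).

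SAP 5.3.1.3 refers missing solicited intensities back to 4.3.1.1 and adds no rule of its own. Protocol 12.3.1 states "No replacement will be done" for safety data and leaves the details to the SAP.

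**The concern.** The investigator's presence field is used as evidence when it says 'No' and is not used when it says 'Yes'. Among infants with no daily records, those reported free of a reaction stay in the denominator and those reported to have had one disappear. Inclusion in the analysis then depends on the outcome being estimated.

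Occurrence of solicited reactions up to Day 7 is a primary safety endpoint (Protocol 9.1.1.2, SAP 4.1). The trial tests no hypotheses, so each group's absolute rate is itself a result. Using the same rule in every group does not correct those rates.

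Such records could arise. Where Day 0 to 7 diary information has not been obtained, Protocol 5.1.4 has the site get it by interviewing the parents at the next visit. That visit is 60 (±14) days after Doses 1 and 2 and 30 (+14) days after Doses 3 and 4. A parent may remember that there was redness or irritability without being able to give a size or grade for any day.

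**Working it through.** The plan states no figure on this point, so there is none to reproduce. The check has three parts: trace the algorithm, establish the direction algebraically, and illustrate the size.

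**Trace, Stage II, all Day 0–7 records missing**

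| Reaction | Investigator field | Daily intensity | Presence | In the analysis? |
|---|---|---|---|---|
| Other than fever | No | None (step 1) | No | Yes, as a non-event |
| Other than fever | Yes | Missing (step 2) | Missing | No |
| Fever | No | Missing | Missing | No |
| Fever | Yes | Missing | Missing | No |

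The asymmetry affects 8 of the 9 solicited terms: 3 injection-site reactions and 5 of the 6 systemic ones. The second row is not written as a rule in the SAP; it is what the written steps produce. One limit applies: an intensity recorded after the solicited period could still give a non-missing presence for the 'D8 and later' display.

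**Direction**

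Let N be infants with daily records, E those among them with the reaction, a the 'No'/all-missing infants and b the 'Yes'/all-missing infants.

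- Rate under the SAP: E/(N+a)
- Rate using both answers: (E+b)/(N+a+b)
- Difference (second minus first): b(N+a−E) / [(N+a)(N+a+b)]

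Since E cannot exceed N, this is never negative. It is positive when b > 0 and E < N+a, and zero when b = 0. Enumerating N from 1 to 39, E from 0 to N, and a and b from 0 to 5 found no case in which the SAP rate was the higher one.

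**Worked example (assumed counts, in a group of 175)**

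N = 165, E = 66, a = 6, b = 4.

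- SAP: 66/171 = 38.6%
- Using both answers: 70/175 = 40.0%
- Dropping both kinds of all-missing record: 66/165 = 40.0%

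The shortfall is 1.4 points.

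**Range (all inputs assumed)**

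Let m be the share of infants with all records missing and p the reaction rate among those with records. Assume that every all-missing infant has a correct investigator entry and that the 'Yes' share among them equals p. The rate using both answers is then p, the SAP rate is p(1−m)/(1−mp), and the shortfall is mp(1−p)/(1−mp).

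| m | p = 10% | p = 40% | p = 70% |
|---|---|---|---|
| 2% | 0.18 | 0.48 | 0.43 |
| 5% | 0.45 | 1.22 | 1.09 |
| 10% | 0.91 | 2.50 | 2.26 |

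(Shortfall in percentage points. For p = 40% and m = 10%: 0.1 × 0.4 × 0.6 / 0.96 = 0.025.)

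If the 'Yes' share among all-missing infants is far above p, the effect is larger. With m = 10%, p = 10% and a 70% 'Yes' share, N = 157.5, E = 15.75, a = 5.25 and b = 12.25. The SAP rate is 15.75/162.75 = 9.7%, against 28/175 = 16.0%, a shortfall of 6.3 points. That is the extreme of the values tried and not an expected size.

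**The case against.** The strongest reply is that these records should hardly exist. Parents get a reminder call 8 days after each vaccination (Protocol 9.1.1.3.2). The visit interview is meant to supply the missing daily data. Missing or discrepant diary entries are clarified verbally (Protocol 13.2), investigators must explain missing information (Protocol 11.1), and consistency checks with queries look for omissions (Protocol 11.2). A 'Yes' with no grade on any day is the kind of omission such checks should find. This stands as a limit on the size. It does not supply a rule for the records that remain.

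A second reply is that the quoted step is sound: a 'No' from the investigator is evidence of absence, and keeping known non-reactors in the denominator is right. This also stands. The bias comes only from what happens to 'Yes'.

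Third, the rule is the same in all randomised groups and no hypothesis is tested. That is correct, and it confines the consequence mainly to absolute rates.

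A reader might infer more than the documents support:

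- That all solicited rates are affected. Fever is excepted in the same sentence, and step 1 does not apply to Stage I. There neither answer is used, so the handling is symmetric.
- That the protocol and SAP contradict each other because the protocol rules out replacement. Protocol 12.3.1 defers the details to the SAP, and SAP 5.3.1 allows imputation in a limited number of situations.

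**Conclusion.** The defect is real and narrow. For Stage II solicited reactions other than fever, the written algorithm uses an investigator 'No' and ignores an investigator 'Yes' when all daily records are missing. The reported Day 0–7 rate can only be lowered by this, and only if 'Yes'/all-missing records occur.

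The size cannot be determined from the documents. About 0.2 to 2.5 points is an illustration for 2% to 10% of infants with all records missing, resting on the assumptions set out with the table; zero is within the possible range. Given the recovery steps at sites, a small effect is likely. It would be wrong to conclude that the rates are known to be understated, or that comparisons between formulations are compromised.

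This is a minor point, but it concerns a primary descriptive safety endpoint. The SAP already treats unsolicited events more consistently: a missing intensity stays missing without removing the event (4.3.1.2.1, 5.3.1.3), and an event with missing time of onset is still included (4.3.1.2.4).

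**What to change.** Add to SAP 4.3.1.1.1 and 4.3.1.1.3, with the same scope as step 1 (Stage II using the diary card, excluding Fever/Pyrexia): when investigator presence is 'Yes' and all daily records are missing, count the reaction as present over Day 0–7, with intensity, time of onset and number of days of presence missing. Report the number of such cases per group.

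The scope limit matters. For fever and for Stage I, a 'No' with all records missing is not set to None. Counting 'Yes' there would use only the positive answers, and rates could then only rise. For fever it would also count an event with no temperature recorded, although fever is defined by temperature.

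The cost is one derivation rule, a missing-grade category in the intensity tables, and slightly less favourable rates if such records exist. No new data are needed, because step 1 already reads the presence field.

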##### 4.3.1.1.2 Maximum Overall Intensity

Maximum overall intensity is derived from the daily intensities computed as described in Section 4.3.1.1.1 and is calculated as the maximum of the daily intensities over the period considered.

##### 4.3.1.1.3 Presence (Occurrence)

Presence is derived from the maximum overall intensity over the time period considered:

- None: No presence
- Grade 1, Grade 2, or Grade 3: Presence
- Missing or Unknown: Missing presence

Participants with at least one non-missing presence for a specific endpoint will be included in the analysis. Conversely, those without a non-missing presence will not be included in the analysis of the endpoint.

The time period is displayed as D0-D3, D4-D7, D8 and later.

##### 4.3.1.1.4 Time of Onset

Time of onset is derived from the daily intensities computed as described in Section 4.3.1.1. It corresponds to the first day with intensity of Grade 1, Grade 2, or Grade 3.

Note: If a reaction is not continuous (ie, reaction occurs over two separate periods of time intervened by at least one daily intensity Missing or None) then the time of onset is the first day of the first presence.

Time of onset period is displayed as, D0-D3, D4-D7.

#### **4.3.1.1.5 Number of Days of Presence (Occurrence)**

Number of days of presence over the period considered is derived from the daily intensities computed as described in Section 4.3.1.1.1. It corresponds to the number of days with daily intensities of Grade 1, Grade 2, or Grade 3. Number of days of presence on the solicited period with a specified intensity may also be derived.

#### **4.3.1.1.6 Number of Days of Presence (Occurrence) During the Solicited Period**

Number of days of presence over the period considered is derived from the daily intensities computed as described in Section 4.3.1.1.1. It corresponds to the number of days with daily intensities of Grade 1, Grade 2, or Grade 3. Number of days of presence on the solicited period with a specified intensity may also be derived.

#### **4.3.1.1.7 Ongoing**

Ongoing is derived from the last daily intensity of the solicited period computed as described in Section 4.3.1.1.1 and the maximum intensity on the ongoing period. The investigator's ongoing flag is not used because the measurement would determine the ongoing status of the reaction.

Ongoing: if the last daily intensity of the solicited period is at least Grade 1 and the maximum intensity on the ongoing period is at least Grade 1.

Not ongoing: if the last daily intensity of the solicited period is None or the maximum intensity on the ongoing period is None.

Missing: all other conditions (in this case, it won't be included in the denominator of the ongoing analysis in the safety tables).

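### With the last daily entry missing, the SAP's ongoing rule for solicited reactions keeps a later None but drops a later Grade 1–3

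*SAP*

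**What the plan says.** SAP 4.3.1.1.7 derives the ongoing status of a solicited reaction from two records and sorts it into three classes.

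- Ongoing requires two conditions together: "last daily intensity of the solicited period is at least Grade 1 and the maximum intensity on the ongoing period is at least Grade 1". Both records must be positive.
- "Not ongoing: if the last daily intensity of the solicited period is None or the maximum intensity on the ongoing period is None". One record of None is enough.
- All remaining combinations are Missing and will not "be included in the denominator of the ongoing analysis in the safety tables".

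The same section sets aside the site's own judgement: "The investigator's ongoing flag is not used because the measurement would determine the ongoing status of the reaction".

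The second record is separate from the daily entries. A note in SAP 4.3.1.1.1 says: "The maximum intensity on the ongoing period is derived from the record of the maximum intensity/measurement after the end of the solicited period". That section also lists Missing (Unknown) as a possible daily value, so a later record can exist when the Day 7 entry does not.

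**The concern.** The later record is treated differently according to what it shows. With the last daily entry missing, a later None is accepted as settling the status and the reaction stays in the denominator. A later Grade 1, 2 or 3 is not accepted, and the reaction leaves both numerator and denominator, although that record is direct evidence that the reaction was present after Day 7. Among reactions with that gap in the diary, those that lasted are removed and those that did not are kept.

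At stake is the percentage of solicited reactions described as continuing past the diary week. It is a descriptive figure, but it is shown by formulation in a Phase II study meant to help select one, and a reader would not see that the exclusions run in one direction.

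**Working it through.** The plan states neither an ongoing percentage nor a rate of missing entries, so there is no figure to reproduce. The check is an enumeration of the rule, then algebra, then an illustration with assumed inputs.

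**Inputs from the documents**

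- The three classes: SAP 4.3.1.1.7. I read the last daily entry as Day 7, since the solicited period runs from Day 0 to Day 7.
- A daily value can be Missing: SAP 4.3.1.1.1.
- No other rule fills a single missing Day 7. Step 1 of SAP 4.3.1.1.1 fills in None, and only for Stage II, not for fever, when all daily entries are missing and the investigator recorded the reaction as absent. SAP 5.3.1.3 only points back to 4.3.1.1.
- Meaning of a solicited grade after Day 7: under Protocol 9.1.1.1 an event starting on Day 8 is unsolicited, so such a grade belongs to a reaction that began by Day 7.

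**Step 1: the nine combinations under the rule as written**

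| Day 7 | Later: Grade 1–3 | Later: None | Later: missing |
|---|---|---|---|
| Grade 1–3 | Ongoing | Not ongoing | Missing, dropped |
| None | Not ongoing | Not ongoing | Not ongoing |
| Missing | **Missing, dropped** | **Not ongoing, kept** | Missing, dropped |

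The two bold cells are the point.

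**Step 2: direction**

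Let a = ongoing with Day 7 present, b = not ongoing with Day 7 present, c = Day 7 missing and later None, d = Day 7 missing and later Grade 1–3.

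- SAP rule: a/(a+b+c).
- Later record used in both directions: (a+d)/(a+b+c+d).
- All Day 7-missing cases dropped: a/(a+b).

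The second minus the first is d(b+c)/[(a+b+c)(a+b+c+d)], which is never negative and is zero if d = 0. The third is never below the first, and the two are equal if c = 0. The SAP figure is therefore never above either symmetric alternative.

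**Step 3: illustrative size (assumed inputs)**

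Let p be the true ongoing share and m the share of Day 7 entries missing at random. Assume every later record is available, and that Day 7 was truly graded whenever the later record is. Then the reported share is p(1−m)/(1−mp), and the relative shortfall is m(1−p)/(1−mp).

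| True p | m = 5% | m = 10% | m = 20% |
|---|---|---|---|
| 5% | 4.76% | 4.52% | 4.04% |
| 10% | 9.55% | 9.09% | 8.16% |
| 20% | 19.19% | 18.37% | 16.67% |

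Over p from 2% to 30% and m from 5% to 30%, the relative shortfall runs from 3.6% to 29.6%.

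In counts: take 100 reactions, 10 persisting, with Day 7 missing for 10, of which 1 persists. Then a = 9, b = 81, c = 9, d = 1. The SAP rule gives 9/99 = 9.09%. Using the later record both ways gives 10/100 = 10.0%. Dropping all ten gives 9/90 = 10.0%.

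**Step 4: where the later-record assumption fails**

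Suppose a later record exists only for reactions that persisted. The 9 non-persisting reactions with Day 7 missing then have neither record and are dropped too, so c = 0. The SAP rule gives 9/90 = 10.0%, which is correct here, while counting the later grade as ongoing gives 10/91 = 11.0%. The case report form would show which situation applies; it is not in the documents.

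**The case against.** The strongest defence is that the asymmetry is ordinary logic. Ongoing is defined as two conditions together, so one None settles the answer and one grade beside an unknown does not. That is true, but it does not explain why unsettled cases should leave the denominator when the record in hand shows presence after Day 7.

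Other objections carry weight:

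- **The later grade is not lost.** SAP 4.3.1.1.3 displays presence for a period of Day 8 and later, which does not depend on Day 7. A reader might infer that persistence is understated throughout the safety tables. The documents do not support that; only the ongoing summary is affected.
- **The status is secondary.** The primary endpoint is occurrence up to Day 7 (Protocol 9.1.1.2), ongoing status is not in the minimum list of parameters in SAP 5.1.1.2, and no hypothesis is tested.
- **Gaps should be few.** Sites obtain outstanding Day 0–7 diary information by interviewing parents (Protocol 5.1.4) and clarify missing diary data verbally (Protocol 13.2).
- **Group comparison.** A reader might infer that a group with less complete diaries would look better. Nothing in a randomised, observer-blind design (Protocol 6.4 and 6.5) suggests unequal completeness.
- **The investigator's flag.** A reader might want the flag to resolve a Day 7 grade with no later record. The SAP rejects the flag with a stated reason, and some of those reactions may have ended on Day 7, so that case can go either way. It is properly left Missing.
- **Wording.** If the last daily entry means the last non-missing one, the two bold cells nearly disappear. The SAP does not say so.

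**Conclusion.** The point holds in a limited form. Read as written, the rule drops a later Grade 1–3 and keeps a later None when the last daily entry is missing. Where both occur, the ongoing percentage is lower than if the later record were used in both directions. The direction follows from the text and from Protocol 9.1.1.1.

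The size cannot be derived from the documents. The percentages in the working rest on assumed values of p and m, entries missing at random and later records being complete. The effect is zero if no last daily entry is missing. If no later None record exists beside a missing Day 7, the rule does no worse than dropping all such cases. This is a low-cost improvement to one descriptive summary and bears on no primary conclusion.

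**What to change.** Amend SAP 4.3.1.1.7:

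- Ongoing: post-period maximum at least Grade 1, and last daily intensity at least Grade 1 or missing.
- Not ongoing: unchanged.
- Missing: all other combinations, including a Day 7 grade with no later record. Do not substitute the investigator's flag.
- Report the number classed Missing per group and reaction next to the ongoing percentages.

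The cost is a wording change and one derivation step on data already collected. There are two small downsides. A reaction that was absent on an unrecorded Day 7 and then returned would be counted as ongoing. If post-period records exist only for persisting reactions, the figure could be slightly high, as in Step 4; the Missing counts would reveal this.
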